8.2. Study Assessments and Procedures

8.2.1. Safety and Screening Assessments

8.2.1.1. Adverse Events

The investigator or site staff is responsible for detecting, documenting, and reporting events that meet the definition of an AE or SAE.

8.2.1.1.1. Definition of Adverse Events

An AE is any untoward medical occurrence associated with the use of a drug in humans, whether or not considered drug related. Therefore an AE can be ANY unfavorable and unintended sign (including an abnormal laboratory finding or vital sign measurement), symptom, or disease temporally associated with the use of a medicinal product, without any judgment about causality.

AEs are recorded from the time that informed consent is signed. Treatment emergent AEs are defined as those that occur on or after the date of the first dose of investigational product.

Events meeting the definition of an AE **include**:

- Exacerbation of a chronic or intermittent pre-existing condition including either an increase in frequency and/or intensity of the condition.
- New conditions detected or diagnosed after investigational product administration even though it may have been present prior to the start of the study.
- Signs, symptoms, or the clinical sequelae of a suspected drug interaction.
- Signs, symptoms, or the clinical sequelae of a suspected overdose of either investigational product or a concomitant medication.
- Clinically significant abnormal findings (laboratory test results, vital signs, physical examination findings, ECGs, radiologic exams, or other studies) should be recorded as AEs. A “clinically significant” finding is one that affects clinical management, including additional visits, monitoring or referrals, diagnostic tests or alteration of treatment, or that is considered clinically significant by the investigator. A clinically significant finding may be a change in a test that has previously been abnormal but now requires additional action.
- When a medical or surgical procedure is performed, the condition that leads to the procedure should be recorded as the AE.

Events that **do not** meet the definition of an AE include:

- Anticipated day-to-day fluctuations or expected progression of pre-existing disease(s) or condition(s) present or detected at the start of the study unless judged by an investigator to be more severe than expected for the subject’s underlying condition.
- Abnormal laboratory, ECG, or vital sign measurements that are not labelled clinically significant (see definition above).

- Situations where an untoward medical occurrence did not occur (social and/or convenience admission to a hospital).
- Overdose in the absence of other AEs will not be reported as an AE in its own right.
- Changes in C-SSRS during the course of the study indicating worsening should be evaluated by the investigator for clinical significance, and if clinically significant (e.g., alteration in medical care or intervention is required), an associated AE should be recorded, if present. The AE should be the primary underlying clinical manifestation assessed as clinically significant, and not the change in score itself.

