4. OBJECTIVES AND ENDPOINTS

Objectives	Endpoints
Primary	
To assess the long-term safety and tolerability of RVT-101	Incidence of AEs and changes in physical examinations, vital signs measurements, ECGs, clinical laboratory assessments, and C-SSRS results
Secondary	
To assess the effects of RVT-101 on subject dependency as measured by the Dependence Scale (DS)	DS score change from baseline at Weeks 28 and 52
To assess the effects of RVT-101 on quality of life as measured by the EuroQOL 5 dimensions questionnaire (EQ-5D)	EQ-5D score change from baseline at Weeks 28 and 52

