8.1. Time and Events

The Time and Events Schedule ([Table 2](#)) displays each study assessment and procedure along with the time of occurrence. V1 of this study may be combined with the final on-treatment visit, V8, of lead-in study RVT-101-3001, or be conducted within 4 weeks of that visit. V2 will occur approximately 4 weeks after V1; V3 and V4 will each occur approximately 6 weeks after the previous visit; subsequent visits will occur approximately every 3 months thereafter. In the event of spontaneously reported tolerability problems, an unscheduled visit will be arranged to assess the subject.

All study assessments should be conducted by the investigator, and/or a suitably qualified designee approved and documented for this study. Information for each visit will be recorded in the source documents and, where appropriate, the eCRF.

V1/Screening/Baseline: The final on-treatment visit, V8, of lead-in study RVT-101-3001 may serve as V1 of this study. If V1 of this study occurs at the same time or within 7 days of V8 of the lead-in study RVT-101-3001, then the procedures conducted for V8 of the lead-in study RVT-101-3001 may serve as the procedures required for V1 of this study and need not be repeated. If V1 of this study occurs greater than 7 days after V8 of the lead-in study RVT-101-3001, then all procedures specified for V1 of this study must be repeated and cannot be combined with the procedures performed on V8 of the lead-in study RVT-101-3001. V1 of this study must occur within 4 weeks of V8 of the lead-in study.

An ICF will be signed by each subject, if he or she is able, or by the subject's legally authorized representative with subject assent before any study-specific procedures are performed. An ICF will also be signed by the caregiver before any study-specific procedures are performed. Subjects will be screened for eligibility according to study inclusion/exclusion criteria at this visit. Eligible subjects will be dispensed investigational product and will be instructed to take it once daily in the morning with or without food.

Subjects who do not qualify for the study during this visit will be considered Screen Failures, and may be rescreened (only once) after discussion with the Medical Monitor. The repeat screening visit must occur within 4 weeks of the original screening visit.

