10.4.2.1. Adverse Events

AEs will be considered treatment-emergent (TEAEs) if they start or worsen after first dose of the open-label treatment. If an AE begins or worsens on the first day of investigational product administration, a CRF and source data note will be provided to clarify whether it occurred prior to or after investigational product administration. TEAEs, SAEs including deaths, AEs that lead to discontinuation of investigational product, and AEs by maximum severity and relationship to investigational product will be summarized by MedDRA system organ class (SOC) and preferred term. TEAEs will also be summarized by preferred term, sorted by decreasing frequency within SOC. AEs will be summarized separately for the Open-Label Treatment Period and the Follow-up Period.

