11.1.5. Study Files and Retention of Records

The investigator must maintain adequate and accurate records to enable the conduct of the study to be fully documented and the study data to be subsequently verified. These documents should be classified into at least the following 2 categories: (1) investigator's study file, and (2) subject clinical source documents.

The investigator's study file will contain the protocol/amendments, eCRF and query forms, IRB or IEC and governmental approval with correspondence, informed consent, drug records, staff curriculum vitae and authorization forms, and other appropriate documents and correspondence.

The required source data should include sequential notes containing at least the following information for each subject:

- Documentation that subject meets eligibility criteria, i.e., history, physical examination, and confirmation of diagnosis (to support inclusion and exclusion criteria);
- Participation in trial (including trial number);

- Trial discussed and date of informed consent;
- Dates of all visits;
- Documentation that protocol specific procedures were performed;
- Results of safety parameters, as required by the protocol;
- Start and end date of investigational product (including dose regimen, dispensing and return);
- Record of all AEs (start and end date, causality and intensity);
- Concomitant medication (including start and end dates, dose, and dose changes);
- Date of trial completion and reason for early discontinuation, if applicable.

All clinical study documents must be retained by the investigator until at least 2 years after the last approval of a marketing application in an ICH region (i.e., United States, Europe, or Japan) and until there are no pending or contemplated marketing applications in an ICH region; or, if no application is filed or if the application is not approved for such indication, until 10 years after the investigation is discontinued and regulatory authorities have been notified. Investigators may be required to retain documents longer if required by applicable regulatory requirements, by local regulations, or by an agreement with Axovant Sciences. The investigator must notify Axovant Sciences before destroying any clinical study records.

Should the investigator wish to assign the study records to another party or move them to another location, Axovant Sciences must be notified in writing in advance.

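### Two treatment-emergent AE rules disagree on pre-dose events on the first dosing day (minor), and the AE percentages would read better with a person-time rate beside them

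*Combined protocol and SAP*

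**What the plan says.** **Treatment-emergent definition.** Section 8.2.1.1.1 uses a calendar-date rule: "Treatment emergent AEs are defined as those that occur on or after the date of the first dose of investigational product". The statistical section, 10.4.2.1, uses a rule tied to the dose itself: "AEs will be considered treatment-emergent (TEAEs) if they start or worsen after first dose of the open-label treatment". For events on the first dosing day, it adds that "a CRF and source data note will be provided to clarify whether it occurred prior to or after investigational product administration".

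**AE incidence.** Section 4 places AE incidence in the primary endpoint: "Incidence of AEs and changes in physical examinations, vital signs measurements, ECGs, clinical laboratory assessments, and C-SSRS results". Section 10.4 gives counts and percentages for categorical data, by lead-in group and overall, and rules out safety inference. Section 10.3.1 defines the Safety Population as everyone with at least one dose, and 10.4.2 bases the safety analyses on it. Section 10.4.2.1 names no AE denominator of its own, and states that "AEs will be summarized separately for the Open-Label Treatment Period and the Follow-up Period". Section 10.4.2 derives duration of exposure but does not link it to AE incidence. Section 10.4.3 leaves additional analyses to the SAP.

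**Follow-up.** Under 6.6.1, permanently stopping product counts as withdrawal and withdrawals are not replaced. AE collection continues after stopping, but no length is given. Section 8.1 specifies the follow-up call for those who complete treatment. Section 8.2.1.1.3 ends routine collection at the follow-up visit and takes later-reported SAEs up to 30 days after the last dose.

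**The concern.** A component of the primary endpoint has two stated counting rules that cannot both apply. The timing note in 10.4.2.1 has no function under a pure date rule. A programmer working from 8.2.1.1.1 and one working from 10.4.2.1 could produce different counts from the same data.

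The second matter is how the percentages will be read. A subject who leaves at Week 10 without an event stays in the denominator like one observed for 52 weeks. In a long-term safety study the percentage is easily taken as a 52-week risk, and it can sit below that risk when people leave event-free. Because lead-in groups are tabulated side by side, unequal dropout alone could also show a gap where the underlying risk is the same.

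**Working it through.** The plan gives no AE rate, dropout rate or hazard shape, so there is no figure to reproduce. The documents supply 364 days of planned treatment (Table 2) and a ceiling of 1150 subjects (10.2). Everything else below is an assumption.

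**1. Can the two definitions give different answers?** AEs are recorded from consent (8.2.1.1.1). Consent and screening belong to V1, where "Eligible subjects will be dispensed investigational product and will be instructed to take it once daily in the morning with or without food". The protocol does not say that the first dose is taken on the V1 day, but this does not matter: whichever day it is, an event earlier on that date is already in the database.

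| AE on the first dosing date | 8.2.1.1.1 | 10.4.2.1 |
|---|---|---|
| Begins before the dose | counted | not counted |
| Begins after the dose | counted | counted |

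The sections also differ on worsening, which the sentence in 8.2.1.1.1 does not mention. That gap is partly closed, because the same section lists exacerbation of an existing condition as an AE.

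**2. How many subjects?** Let p be the 52-week incidence of any TEAE, with constant daily hazard h = −ln(1−p)/364. The date rule adds at most d = 0.5 to 1 day at risk:

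extra = (1−p) × (1 − exp(−h·d))

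- p = 0.5, d = 1: h = 0.6931/364 = 0.00190, so extra = 0.095 points, and 1150 × 0.00095 = 1.1 subjects.
- p from 0.3 to 0.9, d of 0.5 or 1: 0.03 to 0.10 points, or 0.4 to 1.1 subjects.
- First-day hazard five times higher, p of 0.5 or 0.7: about 0.5 points, or 5 to 6 subjects.

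**3. What does unequal follow-up do to a percentage?** Assume a 52-week risk R = 0.10, constant hazard λ = −ln(0.9) = 0.1054 per 52 weeks, and independent dropout D over 52 weeks with μ = −ln(1−D). With no observation after stopping:

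crude = λ/(λ+μ) × (1 − exp(−(λ+μ)))

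At D = 0.2, μ = 0.2231 and exp(−(λ+μ)) = 0.9 × 0.8 = 0.72. So crude = (0.1054/0.3285) × 0.28 = 0.0898.

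If everyone who stops is observed for e = 30/364 longer and those events are counted:

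crude = (1 − exp(−λe)) + λ/(λ+μ) × exp(μe) × (exp(−(λ+μ)e) − exp(−(λ+μ)))

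| Dropout D | Crude % | Relative shortfall | Shortfall with 30 extra days | Subjects missed of 115 |
|---|---|---|---|---|
| 10% | 9.5 | 5.0% | 4.2% | 5.8 |
| 20% | 9.0 | 10.2% | 8.6% | 11.7 |
| 30% | 8.4 | 15.6% | 13.2% | 18.0 |
| 40% | 7.9 | 21.3% | 18.1% | 24.5 |

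The last column is 1150 × (0.10 − crude), with no extra observation.

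- If all events fall in the first 12 weeks (a = 12/52, λ′ = −ln(0.9)/a = 0.4566, exponent taken to a), the shortfall is 1.2% to 5.6%. With 30 extra days it is 0.5% to 2.3%.
- If subjects drop out only after having the event, there is no shortfall.
- Two lead-in groups with the same risk but 10% and 30% dropout would show 9.50% and 8.44%, a gap of 1.1 points. With 575 per group (1150/2, assumed), its standard error is √[(0.0950×0.9050 + 0.0844×0.9156)/575] = 1.7 points.

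**4. How does a person-time rate behave?** Under constant hazard, at-risk time is (1 − exp(−(λ+μ)))/(λ+μ). The rate is then λ, or 10.5 per 100 subject-years, at every D. With all events in 12 weeks, at-risk time is (1 − exp(−(λ′+μ)a))/(λ′+μ) + 0.9 × (exp(−μa) − exp(−μ))/μ. The rate is 11.0 with no dropout and 13.2 at 40%, a rise of 20% while the percentage falls 5.6%.

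**The case against.** The definition conflict is close to editorial. Section 10.4.2.1 is the analysis section, is more specific, and already supplies a way to time first-day events. That stands, and it is why the point is minor. A reader might infer that the TEAE counts are seriously ambiguous, but the arithmetic does not support this. Nor does it help to argue that first-day timing cannot be known because 11.1.5 asks only for AE dates: that list is a minimum, and 10.4.2.1 asks for the timing note separately.

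On incidence, counts and percentages are a valid description in a single-treatment, open-label study with no hypotheses and no safety inference. Section 4 does not define incidence as a 52-week risk, and the all-dosed denominator has to be pieced together from 10.3.1, 10.4 and 10.4.2. All of that stands. A reader might also infer that the plan omits time-adjusted AE summaries altogether. The documents do not show that, because 10.4.3 defers further analyses to the SAP and detailed SAP text was not available for this review.

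Section 10.4.2 also gives part of an answer by deriving exposure. Dividing by total exposure gives about 10.0 per 100 subject-years at every dropout level under constant hazard, which would let a reader see whether dropout explains a group gap. It is still about 5% below the at-risk rate of 10.5, and the protocol does not say the division will be made.

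Finally, the shortfall runs from nil to 21% on assumptions alone, and the illustrated group gap is smaller than its own standard error. That limits the second part to a suggestion.

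**Conclusion.** Minor, in two parts of different standing.

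1. The two definitions contradict each other for an AE on the first dosing date that precedes the dose. This is wrong as written. It moves about 0.03 to 0.10 percentage points, around one subject in 1150, under constant hazard, and 5 to 6 subjects if first-day hazard is five times higher. Confidence in the conflict is high; its practical weight is negligible.
2. The percentages are not an error. Adding a rate that accounts for time at risk is a cheap improvement, subject to what the SAP already contains. The 5% to 21% relative shortfall rests on a 10% risk, constant hazard, independent dropout of 10% to 40%, and no observation after stopping. It shrinks with early events or continued observation, and vanishes if dropout only follows the event.

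A reader might infer that the safety results would be biased or a comparison invalidated. The study tests nothing, so what is affected is how descriptive figures are read.

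**What to change.** 1. Replace the treatment-emergent sentence in 8.2.1.1.1 with the 10.4.2.1 rule, so that one definition governs. How to classify a first-day event whose timing stays unresolved is a detail for the SAP.
2. Check the SAP for a time-adjusted AE summary. If there is none, report beside the percentages, by lead-in group and overall, the number of subjects with a first event per 100 subject-years at risk. Do this for TEAEs, SAEs, deaths and AEs leading to discontinuation. Time at risk runs from first open-label dose to first event in that category or end of AE observation, with the same window in numerator and denominator. The total exposure of 10.4.2 is not that denominator.

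**Cost.** One sentence, one at-risk derivation per event category, and extra table columns. Most inputs are already required source data in 11.1.5: "Record of all AEs (start and end date, causality and intensity" and "Start and end date of investigational product (including dose regimen, dispensing and return", along with visit and trial completion dates. The end of AE observation has to be defined from these, since a last-contact date is not listed by name. The rate assumes a roughly constant hazard and rises by up to 20% in the early-event example at 40% dropout. It therefore supplements the percentages and should not replace them.

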Study Visit Number:	W0	W4	W10	W16	W28	W40	W52	W54			
Study Week:											
Study Day: relative to Baseline unless specified	0	28 ± 7	70 ± 7	112 ± 7	196 ± 7	280 ± 7	364 ± 7	14 to 19 days after last dose of IP		UNS UNS UNS	
Serum chemistry, Hematology, Urinalysis	X	X	X	X	X	X	X			X	
Serum or urine pregnancy test ^b	X						X			X	
DS	X				X		X				
EQ-5D	X				X		X				
Telephone Visit								X			

Abbreviations: AE=Adverse event; C-SSRS = Columbia Suicide Severity Rating Scale; DS= Dependence Scale; ECG = electrocardiogram; EQ-5D= EuroQOL 5 dimensions questionnaire; ET = early termination; IP=investigational product; UNS= unscheduled; V = visit; W = week.

Notes:

- The final on-treatment visit, V8, of lead-in study RVT-101-3001 may serve as V1 of this study. If V1 of this study occurs greater than 7 days after V8 of the lead-in study, then all procedures specified for V1 of this study must be repeated and cannot be combined with the procedures performed on V8 of the lead-in study. V1 of this study must occur within 4 weeks of V8 of the lead-in study.
- Unscheduled visits and/or assessments to occur at the discretion of the Investigator.
- Data for demography, standard medical history, and concomitant medications review at Screening will be rolled over from lead-in study RVT-101-3001.
- Targeted medical history will consist only of ongoing medical conditions and open AEs from the lead-in study, if any.
- Clinical prescription for donepezil will be provided by the Investigator or the treating physician.
- For ET visit only.
- Vital signs will include systolic and diastolic blood pressure, pulse rate, respiratory rate, temperature, and body weight at each visit; height will be performed at screening only.
- Pregnancy test required only for women of child-bearing potential.

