8.2.1.1.2. Definition of Serious Adverse Event

An AE is considered serious if, in the view of either investigator or sponsor, it results in any of the following outcomes:

- Death,
- A life-threatening AE,
(An AE is considered “life-threatening” if, in the view of either the investigator or sponsor, its occurrence places the subject at immediate risk of death. It does not include an AE that, had it occurred in a more severe form, might have caused death. The determination of whether an AE is life-threatening can be based on the opinion of either the investigator or sponsor. Thus, if either believes that it meets the definition of life-threatening, it must be considered life-threatening for reporting purposes.)
- Inpatient hospitalization or prolongation of existing hospitalization,
- A persistent or significant incapacity or substantial disruption of the ability to conduct normal life functions, or
- A congenital anomaly/birth defect.
- Important medical events that may not result in death, be life-threatening, or require hospitalization may be considered serious when, based upon appropriate medical judgment, they may jeopardize the patient or subject and may require medical or surgical intervention to prevent one of the outcomes listed in this definition. Examples of such medical events include allergic bronchospasm requiring intensive treatment in an emergency room or at home, blood dyscrasias or convulsions that do not result in inpatient hospitalization, or the development of drug dependency or drug abuse.

This definition of an SAE permits either the sponsor or the investigator to decide if an event is serious. Because SAEs are critically important for the identification of significant safety problems, FDA believes taking into account both the investigator’s and the sponsor’s assessment is important. For example, the investigator’s perspective may be informed by having actually observed the event, and the sponsor is likely to have broader knowledge of the drug and its effects to inform its evaluation of the significance of the event. If either the sponsor or investigator believes that the event is serious, the event must be considered serious and evaluated by the sponsor for possible expedited reporting.

8.2.1.1.3. Time Period and Frequency for Collecting Adverse Event and Serious Adverse Event Information

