8.2.1.1.7. Reporting of Serious Adverse Events

All SAEs and deaths, regardless of relationship to the study procedures or investigational product, must be reported in English to the study sponsor or sponsor's representatives within 24 hours of the investigators first knowledge of the event through data entry in the SAE eCRF via the electronic data capture (EDC) system. In the event that the EDC system is unavailable, the paper SAE Report form should be used and emailed to Worldwide Clinical Trials Pharmacovigilance (WCT PV) at the following address:

[contact]

In the event that email reporting is not available, site personnel should fax the SAE report to:

[contact]

If notification is made via email or fax, site personnel must then enter the SAE information into the EDC system as soon as the system becomes available.

For the initial SAE notification report, the investigator must provide, at minimum, basic information such as the protocol number, subject's date of birth, subject identification number, period of investigational product intake, event term, nature of the event, the seriousness criteria, and the investigator's attribution regarding relatedness to investigational product. The initial SAE report should include all pertinent known information about the SAE and the affected subject. In addition, the investigator should provide a narrative to describe the course of events including any treatments or relevant procedures. If requested by WCT PV, any missing or additional relevant information concerning the SAE should be entered into the EDC or emailed/faxed to WCT PV.

Follow-up SAE reports may describe the evolution of the reported event and any new assessment of outcome and/or relationship to investigational product. Full supporting documentation should be solicited by the investigative site even if the SAE occurred at another institution. Such documentation may include copies of relevant medical/hospital records, pathology, or autopsy reports.

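### The expected-progression exemption from the adverse event definition has no override for serious outcomes, so non-fatal Alzheimer's-related serious events can be left out of both the AE and SAE tables

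*Combined protocol and SAP*

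**What the plan says.** Section 8.2.1.1.1 lists what is and what is not an AE. Among the inclusions is "Exacerbation of a chronic or intermittent pre-existing condition including either an increase in frequency and/or intensity of the condition". Among the exclusions are anticipated day-to-day fluctuations and the "expected progression of pre-existing disease(s) or condition(s) present or detected at the start of the study unless judged by an investigator" regards the event as unusually severe for that subject's condition. The exclusion covers any condition present at entry and does not treat Alzheimer's disease separately.

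Section 8.2.1.1.2 builds the serious category on the AE definition: "An AE is considered serious if, in the view of either investigator or sponsor, it results in any of the following outcomes". One of the outcomes is "Inpatient hospitalization or prolongation of existing hospitalization". Section 8.2.1.1.7 sets the reporting duty: "All SAEs and deaths, regardless of relationship to the study procedures or investigational product, must be reported in English".

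For events carried over from the lead-in study, a note to Table 2 (section 8.1) says: "Targeted medical history will consist only of ongoing medical conditions and open AEs from the lead-in study, if any". Section 10.4.2.1 then says: "AEs will be considered treatment-emergent (TEAEs) if they start or worsen after first dose of the open-label treatment". The treatment-emergent definition in 8.2.1.1.1 covers AEs that occur from the date of the first dose and does not mention worsening.

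Section 4 names AE incidence in the primary endpoint. It does not name SAEs separately; they are summarised, deaths included, under 10.4.2.1. Section 7.3 confirms that the study is open-label.

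**The concern.** Section 3.1.1 describes Alzheimer's disease as a progressive loss of memory, cognition and daily function with behavioural disturbance. A harmful effect of RVT-101 on behaviour, cognition or function would look much the same. When such an event puts a subject in hospital, the AE definition first asks the investigator whether it was expected. If the answer is yes, nothing in the definition brings the event back on the ground that it was serious.

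The study has no concurrent control and its safety analysis is purely descriptive, so the tables are only as complete as the events entered in them. An event that was never recorded as an AE may not be recoverable at analysis. The rule therefore has to be right while data are being collected.

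**Working it through.** No arithmetic applies: the point concerns event definitions, and the documents give no AE, SAE or hospitalisation rate. The check follows one event through the sections. Take a subject admitted to hospital with worsening agitation or confusion.

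1. **Is it an AE under the inclusion list (8.2.1.1.1)?** Yes, if the worsening is read as greater frequency or intensity of a chronic pre-existing condition.
2. **Is it an AE under the exclusion list (same section)?** No, if the same worsening is read as expected progression. The only way back is an investigator's view that it was more severe than expected. No criterion for *expected* is given, and neither list is said to take precedence.
3. **Does the admission itself satisfy that way back?** Not by the text. The test is severity, and section 8.2.1.1.4 warns that severity and seriousness are different things. No section says that a serious outcome counts as more severe than expected.
4. **Can it be an SAE (8.2.1.1.2)?** Only if it is already an AE. Hospitalisation makes an AE serious; it does not turn a non-AE into an AE.
5. **Must it be reported (8.2.1.1.7)?** That section covers SAEs and deaths. A non-fatal event that is not an AE is neither.
6. **Does it reach a table (10.4.2.1)?** That section summarises AEs and SAEs, so the event appears in neither. The Safety Monitoring Committee (8.2.1.2), which works from accrued safety data, would not see it as an AE.

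By outcome, when the investigator judges the event to be expected progression:

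| Outcome | Result under the current text |
|---|---|
| Death | Reportable under 8.2.1.1.7; summarised with SAEs in 10.4.2.1 |
| Hospitalisation, life-threatening event, incapacity | Can miss both the AE and the SAE tables |
| Non-serious fluctuation or decline | Exempt, as intended |

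The gap is the middle row. The protocol already has a way to label such events without removing them: the causality scale in 8.2.1.1.4 includes grades for events explained by disease.

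The carried-over lead-in AE takes a different path. Entered as targeted medical history, it is a condition present at the start, so the exclusion bullet could be applied to it. Against that, the exacerbation bullet covers an increase in its frequency or intensity, and 10.4.2.1 counts AEs that worsen after the first open-label dose. What remains is inconsistent wording: no order of precedence between the bullets, and a treatment-emergent definition in 8.2.1.1.1 that leaves out the worsening that 10.4.2.1 includes. Two sites could record the same change differently and both be within the protocol.

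**The case against.** The best defence is that the two bullets form a rule and an exception: exacerbation is an AE, the ordinary course of a disease is not, and unusual severity returns an event to AE status. Nearby text supports an intention to capture medical admissions. The only admissions named as non-AEs are those for social reasons or convenience. Clinically significant findings that change management are AEs, as is the condition behind a medical or surgical procedure. The sponsor as well as the investigator may call an event serious. Many Alzheimer's-related admissions would probably be recorded by one of these routes.

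That stands as a reason to expect partial capture. It does not close the gap, because none of these provisions expressly overrides the exclusion, and the sponsor's view on seriousness applies to events already recorded as AEs.

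Other parts of the defence stand in full and limit the point:

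- **Lead-in AEs.** A reader might infer that worsening of open lead-in AEs is exempt and that progressive toxicity is hidden among subjects previously on RVT-101. The documents do not support this. The exacerbation bullet and 10.4.2.1 bring such worsening in, listing an event as medical history does not make its worsening expected, and exclusion criterion 1 screens out subjects whose uncontrolled lead-in AE would preclude continuation.
- **Deaths.** These do not escape, as the table under the check shows.
- **Other evidence of decline.** The Dependence Scale and EQ-5D are not the only sources. Physical and neurological examinations, the C-SSRS, concomitant medication changes and withdrawal reasons are also collected.
- **Use of the exemption.** Applying the exemption can only remove events. But whether knowledge of treatment makes investigators use it more or less often cannot be settled from the documents.

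**Conclusion.** The concern holds in a bounded form and should be fixed. The AE definition lets a non-fatal serious event judged to be expected progression of Alzheimer's disease stay out of both the AE and SAE tables, because an event must be an AE before it can be serious and no sentence makes a serious outcome override the exemption. This bears on AE incidence, part of the primary endpoint, in an uncontrolled open-label study. Separately, worsening of open lead-in AEs is covered but may be recorded inconsistently.

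The size is unknown. The enrolment ceiling of 1150 is the only relevant number in the plan, and with no event rate, and no indication of how often investigators would call an event expected, any count of missed hospitalisations would rest wholly on assumed rates. The conclusion is that the text permits the omission. It does not establish that sites will omit such events, or how many.

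**What to change.** In section 8.2.1.1.1:

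- State that the expected-progression exemption does not apply to any event meeting a seriousness outcome in 8.2.1.1.2. Record such events as AEs and SAEs, with an eCRF flag for *judged expected progression*.
- State that an open lead-in AE that increases in frequency or intensity after the first open-label dose is recorded as an AE.
- Align the treatment-emergent definition with 10.4.2.1, so that both count events that start or worsen.

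In section 10.4.2.1, present the SAE table with and without flagged events, so that readers can see the full count and also discount what investigators considered expected.

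The cost is a wording change, one eCRF flag and one repeated table. The downside is some additional SAE forms, each with the 24-hour reporting duty, and a slightly less favourable SAE incidence. Non-serious fluctuations and expected decline stay exempt, and no treatment rule changes.
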